8.2.6. Patient Global Impression of Severity and Change

In the current study, data collected from the PGIS and PGIC instruments will assist in future analyses of clinically meaningful change for the Abdominal Symptoms domain of the CeD PRO.

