8.2.6.2. Patient Global Impression of Change (PGIC)

Subjects will be asked to complete the PGIC every 2 weeks in the eDiary, beginning 2 weeks after the first dose of study drug administration at Visit 1.

Subjects will be asked to compare their symptoms to those before treatment as follows:

“Please choose the response below that best describes the overall change in your celiac disease symptoms since you started taking the study medication: Much better, A little better, No change, A little worse, Much worse.”

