Symptomatic days will be assessed in terms of the Abdominal Domain, Diarrhea and Loose Stool Domain, and Total GI score of the CeD PRO. A given day is defined as a symptomatic day if any of the domain scores is >0. A day is considered asymptomatic if all of these scores are 0. The number of symptomatic days and asymptomatic days will be derived by month (including baseline) [based on month-based visit windows defined below] and total during the double-blind treatment period (through Week 24).

Weekly Worst Symptom Domain Score in CeD PRO

Weekly worst symptom domain scores will be derived separately for each of the following three domains: 1) Abdominal Domain score, 2) Diarrhea and Loose Stool Domain score, and 3) Total GI score by selecting the worst daily score for all items within each domain for a given week (based on analysis visit windows defined below) and averaging these scores.

BSFS Stools of Type 6 or 7

The BSFS is a pictorial aid to help subjects identify the shape and consistency of their stools during the study (Riegler et al, 2001). The subject will be asked to record the number of stools that have a consistency of Type 6 or 7 (loose stool or entirely liquid) at bedtime daily in the eDiary. On the days in which the subject experiences no such stool (BSFS Type 6 or 7), the subject should record 0 in the eDiary instead of leaving it blank. The sum of weekly stool frequency (sum of the previous 7 days) through Week 24 for stools of BSFS Type 6 or 7 will be calculated, based on the analysis visit windows (defined below). In case of multiple records for stool in one day the latest record in time will be considered.

Baseline Value for Patient-Reported Assessments captured in eDiary

In general, the last non-missing value prior to the first dose of double-blind treatment will be used as the baseline value.

For patient-reported assessments captured in the eDiary, the following definitions of baseline in Table 2 will be used:

Table 2. Definition of Baseline for Patient-Reported Assessments Captured in eDiary

Assessment	Baseline Definition				
CeD PRO (Abdominal domain and other weekly domain scores)	Average of scores from 7 days prior to randomization (e.g., last week of placebo run-in).				
BSFS	Sum of Type 6 or 7 stool experienced over the 7 days prior to the date of first dose of double-blind treatment.				
PGIC/PGIS	Most recent assessment prior to the first administration of double-blind treatment.				

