8.2.2.3 Change from Baseline

Absolute change from baseline is defined as post-baseline value minus baseline value, i.e., a positive sign indicates an increase compared to baseline.

Percent change from baseline is defined as

[(post-baseline value – baseline value) / (baseline value)] x 100.

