The IGA is a 5-point Likert scale designed for use by the Investigator or qualified sub-investigator to assess the subject's clinical disease activity (Inactive Disease, Mild Disease, Moderate Disease, Severe Disease, Very Severe Disease) at each specified time point. Absolute change from baseline to worst post-baseline IGA through Week 24 will be tabulated by treatment group in a shift table. Additionally, this table will be repeated for each subgroup.

Patient Global Impression of Change (PGIC)

Subjects will be asked to complete the PGIC every 2 weeks in the eDiary, beginning 2 weeks after the first dose of placebo, at Visit 1. Subjects will be asked to compare their symptoms to those before treatment as follows:

"Please choose the response below that best describes the overall change in your celiac disease symptoms since you started taking the study medication: Much better, A little better, No change, A little worse, Much worse."

The qualitative responses will be scored quantitatively as 1 = Much better, 2 = A little better, 3 = No change, 4 = A little worse, 5 = Much worse for analysis.

Absolute change from baseline in PGIC through Week 24 will be tabulated by treatment and time point. Additionally, this table will be repeated for each subgroup.

Patient Global Impression of Severity (PGIS)

Subjects will be asked to complete the PGIS every 2 weeks in the eDiary, from the evening of eDiary dispensation at Visit 1 (Day -28) through the end of the study. Subjects will be asked to assess the severity of their symptoms as follows:

"Please choose the response that best describes the severity of your celiac disease over the past 7 days (check one response): None, Mild, Moderate, Severe, Very Severe."

The qualitative responses will be scored quantitatively as 1 = None, 2 = Mild, 3 = Moderate, 4 = Severe, 5 = Very Severe for analysis.

Absolute change from baseline in PGIS through Week 24 will be tabulated by treatment and time point. Additionally, this table will be repeated for each subgroup.

PROACTIVE Dietary Questionnaire

The dietary questionnaire relates to subject's celiac disease during the past 7 days. Subjects will answer the following two questions weekly from Visit 1:

- How many days did you consume a meal prepared outside of your home?
- How many days do you think you consumed gluten?

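### SAP 8.6.3 tabulates PGIC as change from baseline although PGIC is already a change rating, so the tabulated score has no clear meaning within an arm

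*SAP*

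**What the plan says.** The PGIC question, given in Protocol 8.2.6.2 and repeated in SAP 8.6.3, asks for the "overall change in your celiac disease symptoms since you started taking the study medication". The SAP codes the answers "1 = Much better, 2 = A little better, 3 = No change, 4 = A little worse, 5 = Much worse".

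Subjects first answer it in the run-in. The SAP says "beginning 2 weeks after the first dose of placebo, at Visit 1"; Protocol 8.2.6.2 says "beginning 2 weeks after the first dose of study drug administration at Visit 1". The schedule of activities marks PGIC at Visits 2 and 3 and at every later visit. All subjects receive placebo at Visits 1 and 2 and are not told so.

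SAP Table 2 defines the PGIC baseline as "Most recent assessment prior to the first administration of double-blind treatment". SAP 8.2.2.3 sets the general rule: "Absolute change from baseline is defined as post-baseline value minus baseline value". SAP 8.6.3 then plans the table: "Absolute change from baseline in PGIC through Week 24 will be tabulated by treatment and time point", repeated for each subgroup. The paragraph on the severity rating (PGIS) plans its table in the same terms.

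On purpose, Protocol 8.2.6 says that "data collected from the PGIS and PGIC instruments will assist in future analyses of clinically meaningful change" for the Abdominal Symptoms domain, which is the primary endpoint measure.

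**The concern.** Change from baseline suits PGIS, which rates severity over the past 7 days. PGIC is different, because the subject has already made the comparison with an earlier state. Subtracting the run-in rating gives a change of a change, and the value subtracted is a response to placebo given 2 to 4 weeks after Visit 1.

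What is at stake is the readability of one descriptive table and its subgroup repeats. A reader who sees a mean change of, say, zero in an arm cannot tell whether its subjects report being better, the same or worse. The PGIC text names no table of the observed categories that would answer this. SAP 8.6.3 treats other items more fully: Marsh-Oberhuber scores get category frequencies and a shift table, the Investigator Global Assessment gets a shift table, and the weekly worst symptom scores are shown as values as well as changes.

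**Working it through.** The plan gives no figure to reproduce here. The check is to follow the derivation and list its possible results.

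**Inputs.** The codes 1 to 5 (SAP 8.6.3); the baseline P0, the last rating before the first double-blind dose (SAP Table 2); the change rule (SAP 8.2.2.3). With Pt the rating at week t, the tabulated score is D = Pt - P0.

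**All possible pairs.** There are 5 × 5 = 25 pairs (P0, Pt):

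| D | -4 | -3 | -2 | -1 | 0 | +1 | +2 | +3 | +4 |
|---|---|---|---|---|---|---|---|---|---|
| Number of pairs | 1 | 2 | 3 | 4 | 5 | 4 | 3 | 2 | 1 |

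D = 0 comes from five states, from *Much better* at both times (1 - 1) to *Much worse* at both times (5 - 5). D = -1 comes from four pairs, among them *Much worse* to *A little worse* (4 - 5), where the subject still reports being worse.

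**Range allowed by the run-in rating.** The limits are 1 - P0 and 5 - P0:

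| Run-in rating | Lowest D (best) | Highest D (worst) |
|---|---|---|
| 1 *Much better* | 0 | +4 |
| 2 *A little better* | -1 | +3 |
| 3 *No change* | -2 | +2 |
| 4 *A little worse* | -3 | +1 |
| 5 *Much worse* | -4 | 0 |

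A subject at 1 in the run-in can never register benefit. A subject at 5 can never register deterioration.

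**Reference point.** Take a subject who answers *A little better* at the end of run-in and again at week t, so D = 2 - 2 = 0.

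- If the subject counts from Visit 1 on both occasions, 0 means roughly no further change since the end of run-in.
- If the later answer counts from Visit 3, the subject has reported improvement over the run-in and again over the double-blind period, yet D is still 0.

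The run-in is blinded to subjects and PGIC collection is timed from Visit 1, so the first reading is plausible. The wording of the item does not exclude the second.

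**Difference between arms.** For active arm A and placebo arm C:

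mean D(A) - mean D(C) = [mean Pt(A) - mean Pt(C)] - [mean P0(A) - mean P0(C)].

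P0 is recorded before any double-blind dose and after the same placebo run-in, so randomisation makes the second bracket zero in expectation. With complete data, the difference in mean D has the same expectation as the difference in mean observed PGIC. Subtraction can alter precision and the reading within an arm, but it does not shift the comparison.

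**The case against.** The best defence is that D estimates something sensible. If subjects keep Visit 1 as their reference, week t minus end of run-in approximates change since the end of run-in. That is also the span of the primary endpoint, whose baseline is the last run-in week. On that view *Much better* at both times rightly scores 0, and removing run-in placebo response is intended. This stands in part. It requires every subject to use the Visit 1 reference and the five categories to be evenly spaced, and the floor and ceiling limits remain.

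Inclusion criterion 7 excludes subjects whose weekly abdominal scores improve continuously or by more than 50% during run-in. That makes a run-in *Much better* less likely but does not rule it out, because the criterion uses the CeD PRO and not PGIC.

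Protocol 9.4.1 plans summaries of continuous endpoints alongside their changes, so observed mean PGIC might appear anyway. At most this implies means. The PGIC paragraph does not say so, and category counts are not named.

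A reader might infer three stronger things that the documents do not support:

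- *The score is meaningless or ranks subjects wrongly.* A subject going from *A little worse* to *No change* scores -1 and appears to do better than one who is *Much better* throughout (0). That order is wrong only if change since Visit 1 is the target; for change since the end of run-in it is defensible.
- *The treatment comparison is biased.* The identity above shows that it is not, in expectation.
- *PGIC is spoiled as an anchor for meaningful change.* Protocol 8.2.6 refers to future analyses of the collected data. A descriptive table does not alter the stored ratings.

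**Conclusion.** The point holds as a minor correction at exploratory level. As planned, the PGIC table shows a difference of two ordinal change ratings with no clear within-arm meaning: one value covers opposite states, the attainable range is set by the run-in answer, and interpretation turns on a reference point that the SAP does not state.

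Its reach is limited. PGIC is among the other efficacy variables, its paragraph plans a table with no model or test, and primary, secondary and safety results are unaffected. The conclusion that arm comparisons are unbiased rests on randomisation and complete PGIC data. How many subjects rate themselves *Much better* or *Much worse* in the run-in, and how many count from Visit 3, cannot be known from the documents, so the practical distortion cannot be sized beyond the limits tabulated above.

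The exploratory endpoint wording is redacted. Whether the protocol also frames PGIC as change from baseline cannot be checked, and nothing is inferred from that.

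**What to change.** In SAP 8.6.3, replace the PGIC change-from-baseline table with counts and percentages of the five observed categories by treatment and visit, overall and for each subgroup. Add the mean score if wanted. Show the run-in PGIC separately, and drop the use of Table 2 to derive a PGIC change. State that the rating is taken to refer back to Visit 1, and acknowledge that some subjects may have counted from Visit 3. Leave change from baseline in place for PGIS.

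For later work on meaningful change, use the observed PGIC category matched to CeD PRO change over the same span (from Visit 1), or use change in PGIS as the anchor.

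The cost is a few lines of SAP text and one table shell. No new data are needed, and no other analysis changes.

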8.7 Analysis of Safety and Tolerability

All analyses of safety and tolerability will be conducted on Safety analysis set, if not specified otherwise.

8.7.1 Extent of Exposure

The number and percentage of subjects who received 0, 1, 2, 3, or 4 injections at each visit will be summarized by treatment group.

Dates and times of subcutaneous (SC) injections will be listed by subject.

Additionally, the number and percentage of subjects who received 0, 1, 2, 3, or 4 injections at each visit will be summarized for the run-in period using the RIS analysis set.

The dates and times of the subcutaneous (SC) injections during the run-in period will be listed by subject.

8.7.2 Adverse Events

Adverse Events (AEs) and serious adverse events (SAEs) are collected from the signing of the ICF until final visit (Visit 16) and will be classified by System Organ Classes (SOC) and Preferred Terms (PT) using the latest MedDRA dictionary applicable at the time of database lock.

Treatment-emergent adverse events (TEAEs) are collected from the first dose of double-blind study drug until the last dose of double-blind study drug + 42 days. The AEs and SAEs reported during the screening period (those which started after the first screening visit and ended before the start of run-in period or ongoing at the time of run-in period) and single-blind placebo run-in period AEs and SAEs (those which started after visit 1 (first run-in period visit) and ended before the start of double-blind randomized treatment period or ongoing) will be reported separately from the TEAEs.

AEs reported during post-treatment period, i.e. starting at the end of treatment emergent period will be summarized by System Organ Classes (SOC) and Preferred Terms (PT).

Injection site reactions are those identified programmatically using the MedDRA High Level Term of "Injection site reactions".

Adverse Events of Special Interest (AESI) are (1) severe opportunistic infections and (2) hypersensitivity reactions of at least moderate severity. AESI will be programmatically identified for summarization based on the criteria below using MedDRA Preferred Term or Standardized MedDRA Queries (SMQ) (narrow) which also meet severity/seriousness criteria in the eCRF:

Table 3 AESI Criteria

AESI Category	eCRF AE page	MedDRA Search Terms
Severe opportunistic infections	"Severe" or Serious noted in eCRF	PT included in SMQ (narrow) of Opportunistic infections (SMQ) (20000235)
Hypersensitivity reactions of at least moderate severity	"Moderate", "Severe", or Serious noted in eCRF	PT contains "Hypersensitivity" or "hypersensitivity" OR PT included in SMQ (narrow) of • Anaphylactic reaction (SMQ) (20000021) • Hypersensitivity (SMQ) (20000214) • Severe cutaneous adverse reactions (SMQ) (20000020) • Drug reaction with eosinophilia and systemic symptoms syndrome (SMQ) (20000225) • Angioedema (SMQ) (20000024)

An overall summary table of treatment-emergent adverse events will be produced and will present the number and proportion (%) of subjects in each treatment group who have at least one adverse event in the following categories:

- TEAE
- TEAE related to study drug (possible, probable, or definite attribution)
- TEAE severity (mild, moderate, severe)
- TEAE leading to study treatment discontinuation
- TEAE leading to death
- · Treatment-emergent injection site reactions
- Treatment-emergent SAE
- Treatment-emergent AESI

In case of more than one reported severity (e.g., mild, moderate, severe) and/or causality (e.g., unrelated, unlikely, possible, probable, definite) the worst outcome is used for reporting, respectively.

Summary tables presenting the number and proportion (%) of subjects in each treatment group who have at least one adverse event in the following categories will be presented by SOC and PT:

- TEAE
- AEs occurring during the Screening period (All Screened analysis set)
- AEs occurring during the Run-in period (Run-in analysis set)
- TEAE related to study drug (possible, probable, or definite attribution)
- Severe TEAE
- TEAE leading to study treatment discontinuation
- TEAE leading to death

- Treatment-emergent injection site reactions
- Treatment-emergent SAE
- SAE occurring during the Screening period (All Screened analysis set)
- SAE occurring during the Run-in period (Run-in analysis set)
- Treatment-emergent AESI

For the summaries of severe TEAE, serious TEAE, treatment-emergent AESI, and TEAE leading to study treatment discontinuation, the risk differences (comparing PRV-015 arms to placebo) and exact 95% CI (using the Clopper-Pearson method) will be provided for each SOC or PT.

A summary table presenting the number and proportion (%) of subjects in each treatment group who have at least one TEAE will be presented by descending frequency of PT.

For summary tables by SOC/PT or by PT, subjects will be counted once in the applicable row.

Data listings will also be provided for AEs and SAEs occurring during Screening and Run-in periods, respectively. Additional data listings of TEAEs will be provided.

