7 ESTIMATION OF SAMPLE SIZE

A proposed sample size of approximately 50 evaluable subjects within each treatment group would provide approximately 80% power to detect a 0.40 difference from placebo and any given active treatment group at the two-sided, 0.05 level of significance in the primary endpoint, change through Week 24 in the Abdominal Symptoms domain score in CeD PRO. These calculations are based on the assumption of a within-subject standard deviation (SD), as derived in the CELIM-NRCD-001 trial using the mixed effect modelling for repeated measures (MMRM) analyses. An approximate difference in the overall least squares (LS) means through 16 weeks in the treatment period was observed between the active (300 mg) and placebo groups. The overall estimate through 16 weeks was observed to be for placebo versus for the 300 mg treatment group. Of note, the estimated difference at week 16 was however, the more conservative overall difference of was used in the calculation of sample size. The results and their ranking are exploratory in nature, and the selection of endpoints and dose for confirmatory studies will be based on the totality of evidence. As such, these calculations are not adjusted for multiplicity.

Approximately 220 subjects will be randomized at a ratio of 1:1:1:1 to PRV-015 100 mg, 300 mg, 600 mg, or placebo (approximately 55 subjects per group). Subjects will be stratified by normal or abnormal baseline VH:CD (i.e., <2 or \ge 2) and by the CeD PRO Abdominal Symptoms domain score of <3 or \ge 3 at baseline using the average of the Abdominal Symptoms domain scores over the last week of the single-blind placebo run-in period immediately before

Confidential Page

randomization. The number of subjects with Marsh score 0 or 1 will be capped at approximately 72. Withdrawn subjects will not be replaced.

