8.1.8 Safety analysis set

The safety analysis set includes all subjects who take at least 1 dose of the study drug postrandomization. Subjects will be analyzed according to the treatment they actually received. Any subject randomized to placebo who incorrectly receives one or more doses of PRV-015 will be analyzed as receiving PRV-015 and any subject randomized to PRV-015 who incorrectly only receives placebo doses will be analyzed as receiving placebo. If any subject received multiple PRV-015 dose levels, subject will be analyzed at the highest dose received.

Overview of the different analysis sets, and their usage is presented in Table 1. Data listings will primarily present all randomized subjects' data (i.e. based on ITT population)

	ALL	RIS	ш	mIT	PP*	PK	IMG	Safety
Disposition	X							
Demographics and baseline characteristics			X	X	X			
Primary efficacy endpoint, primary analysis				X	X			
Primary efficacy endpoint, sensitivity analyses				X				
Primary efficacy endpoint, subgroup analyses				x				
Secondary efficacy endpoints				X	x			
Secondary efficacy endpoints, subgroup analyses				x				
Other efficacy endpoints				X				
Secondary safety endpoints (single-blind placebo run-in period)		X						
Secondary safety endpoints (post-randomization period)								X
Secondary Pharmacokinetics Endpoints						X		
Secondary Immunogenicity Endpoints							X	

^{*} Additional analysis on PP analysis set may be added where deemed necessary.

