8.2 General Statistical Considerations

Single-blind placebo run-in period is defined as a period for 4 weeks, starting at visit 1.

Treatment emergent period is defined from the first dose of double-blind study drug at visit 3 until the last dose of double-blind study drug + 42 days (i.e., to the end of 4-week safety follow-up period).

Post-treatment period is defined from the end of treatment emergent period.

All outputs are summarized by treatment and visit, if applicable.

Outputs will generally use the following header structure (label and order):

Placebo	PRV-015 100 mg	PRV-015 300 mg	PRV-015 600 mg
N = xx	N = xx	N = xx	N = xx

Total of PRV-015 groups is added for safety and baseline outputs or where relevant in the following way:

Placebo	PRV-015 100 mg	PRV-015 300 mg	PRV-015 600 mg	Total PRV-015
N = xx	N = xx	N = xx	N = xx	N = xx

All statistical tests will be two-sided at the 0.05 level of significance without multiplicity adjustment. In addition to the inferential statistics, 95% confidence intervals will be constructed.

Various covariates will be included in the models and will be retained in the respective models regardless of their significance or lack thereof. The list of variables to be included is described in detail in the following sections.

SAS codes provided in the appendix 11.4 may be modified based on statistical considerations, without requiring SAP amendment.

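### SAP 8.7.2 names Clopper-Pearson, a one-sample method, for the confidence interval of adverse-event risk differences; a two-sample method should be named

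*SAP*

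**What the plan says.** SAP 8.7.2 first lists the tables concerned: "For the summaries of severe TEAE, serious TEAE, treatment-emergent AESI, and TEAE leading to study treatment discontinuation". For these it promises that "the risk differences (comparing PRV-015 arms to placebo) and exact 95% CI (using the Clopper-Pearson method) will be provided for each SOC or PT". They are the only adverse-event tables for which the section asks for a comparison with placebo; the rest are counts and percentages by arm.

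The arms are independent parallel groups analysed as treated: "The safety analysis set includes all subjects who take at least 1 dose of the study drug postrandomization". The planned size is "approximately 55 subjects per group" (SAP 7).

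Nothing elsewhere supplies an interval method for a difference in proportions:
- SAP 8.2 promises 95% confidence intervals in general without naming a method, and sets the framework: "All statistical tests will be two-sided at the 0.05 level of significance without multiplicity adjustment".
- SAP Appendix 11.4 has code for the repeated-measures model, multiple imputation, ANCOVA, Levene, chi-square and Cochran-Mantel-Haenszel analyses, but none for a risk difference.
- SAP 8.10, on changes from the protocol, does not mention it.
- Protocol 9.4.5 plans only tabulation.

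**The concern.** The sentence attaches a method for a single binomial proportion to the difference of two proportions. Clopper-Pearson takes one count out of one denominator. Its limits describe one arm and cannot fall below zero, whereas a risk difference can.

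A programmer would have to guess what was meant. The text could mean Clopper-Pearson limits for each arm, which leave the difference with no interval. It could mean some combination of the two sets of limits. Or it could mean an exact unconditional interval for the difference, whose width depends strongly on the test statistic, and that is not stated.

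Severe, serious and special-interest events broken down by preferred term are likely to be sparse, which is where these readings diverge most. Two analysts could both follow the sentence and report different intervals, or the method could be settled after unblinding.

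**Working it through.** There is no stated figure to reproduce, so the check is what each reading of the sentence would print.

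**Inputs.** n = 55 per arm (SAP 7); 95% two-sided (SAP 8.2 and 8.7.2). Event counts and rates are assumptions, because the documents give none for these tables.

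**Step 1: Clopper-Pearson itself.** For x events in n, the limits are the 2.5% quantile of Beta(x, n-x+1) and the 97.5% quantile of Beta(x+1, n-x). For x = 0 the upper limit is 1 - 0.025^(1/55) = 6.49%.
- Active 5/55: 3.02% to 19.95%
- Placebo 0/55: 0% to 6.49%

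The risk difference is 5/55 - 0/55 = 9.1%. Neither interval is an interval for it.

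**Step 2: forcing a difference out of two Clopper-Pearson intervals.** The ad hoc route is to subtract opposite limits: lower = active lower - placebo upper, upper = active upper - placebo lower. For 5 v 0 this is 3.02 - 6.49 = -3.5% to 19.95 - 0 = 20.0%. Exact coverage at n = 55 is 99.99% at true rates of 5% v 2%, 99.8% at 10% v 5% and 99.7% at 20% v 10%. This is not a 95% interval.

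**Step 3: exact unconditional intervals for the difference.** For each hypothesised difference, all 56 x 56 possible tables are enumerated, the one-sided p-value is maximised over the unknown common nuisance rate, and differences with p > 0.025 on each side are kept. Two test statistics are compared: the score statistic (variance from the constrained maximum-likelihood estimates) and the raw difference x1/n - x0/n. Miettinen-Nurminen, an asymptotic interval, is shown for reference.

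| Active v placebo events | Score-based exact | Raw-difference exact | Miettinen-Nurminen |
|---|---|---|---|
| 4 v 0 | 0.3% to 17.6% | -12.3% to 26.4% | 0.5% to 17.3% |
| 5 v 0 | 1.7% to 20.0% | -10.5% to 28.1% | 2.2% to 19.6% |
| 7 v 1 | 1.0% to 22.9% | -8.7% to 29.9% | 1.5% to 22.5% |
| 0 v 0 | -6.8% to 6.8% | -19.4% to 19.4% | not computed |

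**Step 4: where zero is first excluded.** With no placebo events, the maximised one-sided p at zero difference is:
- Score: 0.046 at 3 v 0 and 0.022 at 4 v 0, so 4 events (4/55 = 7.3%)
- Raw difference: 0.035 at 10 v 0 and 0.022 at 11 v 0, so 11 events (11/55 = 20.0%)

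The raw-difference value can be confirmed by hand. Its worst case is a common rate of 50%, where the difference in counts has SD sqrt(2 x 55 x 0.25) = 5.24. With continuity correction, 10.5/5.24 = 2.00 gives p of about 0.023, and 9.5/5.24 = 1.81 gives about 0.035. The interval is wide because it guards against a background rate far from that of rare events.

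With 0, 1 or 2 placebo events the thresholds are 4, 7 and 8 (score) against 11, 12 and 13 (raw).

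**Step 5: operating characteristics.** Coverage over nine rate pairs from 1% v 1% to 20% v 10% is 95.5% to 99.7% (score-based exact), 99.7% to 100% (raw-difference exact) and 94.8% to 99.7% (Miettinen-Nurminen). The probability that the lower limit exceeds zero is:

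| True rates | Score-based exact | Raw-difference exact | Miettinen-Nurminen |
|---|---|---|---|
| 5% v 1% | 17.7% | 0.0% | 17.7% |
| 10% v 2% | 42.2% | 1.0% | 42.2% |
| 20% v 10% | 29.8% | 8.9% | 31.1% |

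With 50 per arm the zero-placebo thresholds stay at 4 and 11. At 10% v 2% the score-based and raw-difference probabilities become 37.1% and 0.5%.

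**The case against.** The strongest reply is that the contrast of 4 against 11 events does not come from the SAP, which names neither an unconditional interval nor a raw-difference statistic. Among methods most statisticians would choose, the spread is small: score-based exact and Miettinen-Nurminen differ by about half a percentage point in the table above and share the same threshold at 4 v 0. This stands. The contrast shows how much *exact* leaves open, not the effect of Clopper-Pearson as such. The literal attempt to use Clopper-Pearson still differs, however: subtracting limits at 5 v 0 includes zero (-3.5%), while the score-based interval does not (1.7%).

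The assumed rates may also be high. Protocol 2.3 describes adverse reactions identified so far as mild and transient, so many rows could hold 0 to 3 events, and at 3 v 0 even the score-based interval includes zero. This is fair, and the counts and rates are illustrations only.

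A charitable reader may take Clopper-Pearson to refer to each arm's incidence. The sentence does not say so, and on that reading the risk difference has no named interval, so the same edit is needed.

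SAP 8.2 adds that "SAS codes provided in the appendix 11.4 may be modified based on statistical considerations, without requiring SAP amendment". That does not help, because the appendix has no risk-difference code and the error is in the text of 8.7.2.

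Finally, the choice among two-sample methods is partly preference. That is accepted: what is established is that one must be named.

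**Conclusion.** The point holds. As written, the rule cannot be carried out for the quantity it is meant to describe, and no other section repairs it. That conclusion follows from the definition of the method and rests on no assumed figure.

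The numerical size does rest on assumptions: 55 per arm and invented event counts. On those, the printed interval and the point at which it excludes zero can differ materially between readings that all claim to be exact.

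The consequence for the trial is minor. The intervals go beyond the tabulation planned in Protocol 9.4.5, no safety decision depends on them, there is no multiplicity control, and counts by arm let any reader recompute a valid interval. The correction is worth making before unblinding, since Protocol 9.4 expects the analyses to be described in detail by then.

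**What to change.** In SAP 8.7.2, replace the method phrase so that the text provides, for each SOC or PT, the risk difference (each PRV-015 arm minus placebo) with its exact unconditional 95% confidence interval based on the score statistic. If Miettinen-Nurminen limits are preferred, name them and delete *exact*, because that interval is asymptotic. Use Clopper-Pearson only where single-arm incidence is shown, and label it as such. Adding code to Appendix 11.4 is optional.

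The cost is one sentence, with no change to data collection or the efficacy analyses. The score-based exact interval is slightly wider than Miettinen-Nurminen, as the 5 v 0 and 7 v 1 rows of the first table show. At 20% v 10% it excludes zero a little less often (29.8% against 31.1%).
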